5.4. Dosing Rationale

The dose of 400 mg q.d. GLPG3970 will be used in this study.

5.5. Potential Risks and Benefits

GLPG3970 has been studied in a nonclinical setting (Section 2.1) and is being studied in a FIH study (Section 2.2) where the single and multiple ascending dose parts of the study are completed up to the dose of 400 mg q.d. GLPG3970 was well tolerated at all dose levels studied in the FIH study. Study GLPG3970-CL-209 is the first study where GLPG3970 is being administered to subjects with RA.

GLPG3970 has a novel dual mechanism of action, which is intended to restore the balance of the immune system by reducing several mediators of inflammation and by improving immune-regulatory mechanisms that may be impaired in autoimmune diseases such as, for example, RA, psoriasis, and inflammatory bowel disease. Thus, this may weaken the immune response and can potentially increase subject's risk to developing infections (opportunistic infections, SARS-CoV-2, etc). Careful monitoring and reporting of signs and symptoms is therefore required, to enable prompt medical evaluation and pharmacological or clinical intervention.

Based on the mechanism of action of GLPG3970 and its potential to control pro-inflammatory and immunomodulating cytokines, such as TNF α and IL-10, an improvement of clinical symptoms of RA may be derived.

Risk Mitigation

Mitigation measures have been taken to ensure safety of the subjects targeting population selection, dose, concomitant medications, and safety surveillance on certain laboratory parameters and biomarkers. Information on important safety risks is included in the latest version of the IB.

In the forthcoming study subjects' risk will be minimized by implementing conservative eligibility criteria, including RT-PCR testing to exclude subjects with SARS-CoV-2, by standard laboratory tests, by collecting TEAEs throughout the study, and monitoring of subjects for infection symptoms. Any potential negative effects of GLPG3970 will be carefully assessed through regular physical assessments and laboratory monitoring that will happen at every visit. Laboratory alerts will be set up for the study in order to early inform the study investigator and the sponsor on highly abnormal laboratory values (severity Grade 3 and above). A Data Safety Monitoring Committee will monitor unblinded data.

- [REDACTED]
- The selection of the dose proposed for this study lies within the exposure safety limits, defined based on nonclinical safety studies, and exposures previously shown to be safe and well tolerated in healthy male subjects.
- [REDACTED]

For more details refer to the latest version of the IB and its relevant updates/addenda.

Subjects at risk of tuberculosis, HIV positive subjects, subjects testing positive for hepatitis B or C and subjects tested positive for SARS-CoV-2 are excluded from the study. Given this study

may be performed during a SARS-CoV-2 pandemic, the age limit of participants was set to 65 years of age and appropriate measures should be taken to minimize the risk of SARS-CoV-2 infection for subjects participating in the study as well as study site personnel. Local guidelines to prevent SARS-CoV-2 infection should be adhered to and a leaflet should be made available for all subjects detailing the SARS-CoV-2 safety measures to be taken.

In case a randomized subject is not available to attend a scheduled study visit on site due to SARS-CoV-2 travel restrictions, a phone call or a televisit may be conducted instead. It is strongly recommended to conduct planned study assessments for the applicable visit as per protocol as much as possible. If possible and if local regulations allow and the subject agrees, trained study staff or trained personnel are encouraged to collect study assessments at the study subjects' home or a local facility if social distancing and hygiene rules can be applied.

Only staff trained in conducting the protocol planned assessments are authorized to perform home or local facility visit assessments and the alternative arrangements need to be adequately documented. Direct to patient (DTP) shipments are possible if needed. Subjects presenting with signs and symptoms of infection, including SARS-CoV-2 infection should immediately contact the site investigator, who should inform the sponsor's medical responsible as soon as possible, and SARS-CoV-2 testing should be performed.

6. CLINICAL STUDY POPULATION

6.1. Inclusion Criteria

Subjects must meet all of the following inclusion criteria to be eligible for participation in this study:

1. Male or female subject ≥ 18 and < 65 years of age, on the date of signing the ICF.
2. A body mass index (BMI) between 18–32 kg/m², inclusive.
3. Diagnosis of RA ≥ 6 months prior to screening AND meeting the 2010 ACR/EULAR criteria of RA AND ACR functional class I-III.
4. Have ≥ 6 swollen joints (from a SJC66) AND ≥ 8 tender joints (from a TJC68) at screening and at the baseline visit (Visit 1) prior to the first IP dosing.
5. DAS28 (CRP) > 3.2 (moderate disease) at screening.
6. Screening serum high sensitivity CRP (hsCRP) $>$ upper limit of normal (ULN, central laboratory reference: ≤ 5.0 mg/L).
7. Inadequate response to MTX, i.e. treatment-experienced subjects who demonstrated inadequate clinical response during treatment with MTX.
8. Have received MTX for ≥ 6 months and on stable dose (10 to 20 mg/week) of MTX for at least 4 weeks prior to screening and willing to continue on their current stable dose and dosing regimen for the duration of the study.
9. If taking systemic steroids, prednisone equivalent at a dose of ≤ 10 mg/day and stable for at least 4 weeks prior to the first IP dosing.
10. If taking non-steroidal anti-inflammatory drugs (NSAIDs), these must be at a stable dose for at least 2 weeks prior to first IP dosing.
11. Female subjects of childbearing potential must have a negative highly sensitive (serum beta human chorionic gonadotropin) pregnancy test at screening. Female subjects of non-

childbearing potential must have a negative FSH test at screening or must be at least 6 months permanently surgically sterile (bilateral oophorectomy, i.e. surgical removal of ovaries, bilateral salpingectomy or hysterectomy, i.e. surgical removal of uterus).

12. Female subject of child bearing potential or male subject must agree to use highly effective contraception/preventive exposure measures (as described in Section 6.3.1).
13. Able and willing to comply with the CSP requirements (e.g. opening and reconstituting the IP formulation) and must sign and date the ICF as approved by the Independent Ethics Committee (IEC) / Institutional Review Board (IRB), prior to any screening evaluations.
14. Able and willing to comply with restrictions on prior and concomitant medication as described in Section 6.3.2.

6.2. Exclusion Criteria

Subjects meeting one or more of the following criteria cannot be enrolled in this clinical study:

1. Current therapy with any conventional DMARD other than MTX, including
 - a. Oral or injectable gold, sulfasalazine, antimalarials, azathioprine, or D-penicillamine within 4 weeks prior to screening,
 - b. Cyclosporine within 8 weeks prior to screening, and
 - c. Leflunomide within 3 months prior to screening or a minimum 4 weeks prior to screening if after 11 days of standard cholestyramine therapy.
2. Current or previous treatment with a bDMARD. Except for subjects who received bDMARDs only in a single clinical study setting:
 - a. For whom the last dose of bDMARD \geq 6 months prior to screening (12 months for rituximab or other lymphocyte depleting agents), AND;
 - b. For whom the bDMARD was effective, without being discontinued due to lack of efficacy.
3. Subjects who received an intra-articular or parenteral corticosteroid injection within 4 weeks prior to screening.
4. Subjects who received a prior surgical intervention within 12 weeks prior to screening or likely requirement for surgery during the study.
5. Subject has a history of tuberculosis (TB) diagnosis or evidence of active or latent infection with *Mycobacterium tuberculosis* as defined by one of the following assessments:
 - a. Positive QuantiFERON-TB Gold test result at screening, OR
 - b. Chest radiograph (posterior anterior view) taken within 12 weeks prior to screening, read by a qualified radiologist or pulmonologist, with evidence of current active TB or old inactive TB.
6. Subject has any active systemic infection within 2 weeks prior to first IP dosing, or poorly controlled chronic cardiac, pulmonary, or renal disease.
7. Subject has a known or suspected history of or a current immunosuppressive condition, or a history of invasive opportunistic infections (e.g. HIV infection, histoplasmosis, listeriosis, coccidioidomycosis, pneumocystosis, aspergillosis).
8. Subject has a chronic hepatitis B virus (HBV) infection, as defined by persistent HBV surface antigen (HBsAg) positivity. Subject has hepatitis C virus (HCV) infection, as defined

by positive HCV antibody at screening and detectable HCV viremia. Subjects with positive HCV antibody must undergo reflex HCV RNA testing, and subjects with HCV RNA positivity will be excluded. Subjects with positive HCV antibody and negative HCV RNA are eligible.

9. Subject testing positive at screening for SARS-CoV-2 infection as detected by real time polymerase chain reaction (RT-PCR), subjects presenting any signs or symptoms as detected at baseline following careful physical examination (e.g. cough, fever, headaches, fatigue, dyspnea, myalgia, anosmia, dysgeusia, anorexia, sore throat, others) or reporting any signs and symptoms for the 2 preceding weeks, or subjects who have been exposed to individuals with confirmed or suspected diagnosis of SARS-CoV-2 within 2 weeks prior to baseline (BMJ, 2020) (BMJ, 2020). In addition, any other locally applicable standard diagnostic criteria may also apply to rule out SARS-CoV-2 infection.
10. Investigator or other study staff or relative thereof who is directly involved in the conduct of the study.
11. Subject has any condition or circumstances that, in the opinion of the investigator, may make a subject unlikely or unable to complete the study or comply with study procedures and requirements.
12. Subject has a known hypersensitivity to IP ingredients or history of a significant allergic reaction to IP ingredients as determined by the investigator.
13. Subject has any illness, judged by the investigator as relevant for participation in the study, in the 3 months prior to the first dose of the IP.
14. Subject has presence or sequelae of gastrointestinal, liver, kidney (creatinine clearance $[ClCr] \leq 90$ mL/minute, for elderly ≤ 60 mL/minute, using the Cockcroft-Gault formula: if calculated result is ≤ 90 mL/minute, for elderly ≤ 60 mL/minute, if applicable, a 24-hour urine collection can be used) or other conditions known to interfere with the absorption, distribution, metabolism, or excretion of drugs.
15. Subject has a history of malignancy within the past 5 years prior to screening with the exception of excised and curatively treated non-metastatic basal cell carcinoma or squamous cell carcinoma of the skin or carcinoma in situ cervix which is considered cured with minimal risk of recurrence.
16. Subject concurrently participates or participated in a drug, drug/device or biologic investigational research study within 3 months or 5 half-lives of the IP, whichever is longer, prior to screening.
17. Subject has a history or presence of clinically significant abnormalities detected on 12-lead ECG of either rhythm or conduction e.g. known long QT syndrome or a QTcF >450 ms (male), >460 ms (female) detected on the 12-lead ECG. A first-degree atrioventricular block will not be considered as a significant abnormality.
18. Female subject is breast feeding or intending to become pregnant or breastfeed during the study.
19. Subject was vaccinated with a live vaccine within 60 days prior to screening.

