4.3. Other Endpoints

5. INVESTIGATIONAL PLAN

5.1. Clinical Study Design

This is a Phase 2, randomized, double-blind, placebo-controlled, multicenter parallel-group study evaluating GLPG3970 in adult subjects with moderately to severely active RA and an inadequate response to MTX. In this study, subjects will receive 1 dose level of GLPG3970 (400 mg once daily [q.d.]) or placebo on top of their stable dose and dosing regimen of MTX.

The study is planned to randomize 25 subjects in a 3:2 ratio (15 subjects planned to receive GLPG3970 and 10 subjects planned to receive placebo).

The study will consist of 3 study periods:

- Screening period: up to 3 weeks with 1 study visit.
- Double-blind treatment period: 6 weeks with 4 study site visits (Days 1, 15, 29, and 43) and 1 telephone call (Day 8).
- Follow-up (FU) period: 2 weeks with 1 study visit.

Subjects will participate in the study for a maximum of 11 weeks (screening to FU) and will receive oral GLPG3970 or placebo, as a reconstituted oral solution, q.d. for 6 weeks.

Refer to the Schedule of Activities (Section 8.11) for further details.

A schematic diagram of clinical study design, procedures and stages is provided in [Figure 1](#).

[figure not shown]

Figure 1 Schematic Diagram

For detailed information regarding dosage form, packaging and labeling of the investigational product (IP) refer to Section 7.2, “[Dosage and Administration](#)” and Section 7.3, “[Packaging, Labeling and Distribution](#)”.

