6.3.2. Prior and Concomitant Medications

Prior and concomitant therapies taken for long term treatment of pre-existing conditions are allowed, provided they are in accordance with the inclusion and exclusion criteria (see Section 6.1 and Section 6.2, respectively) and with the prohibitions and restrictions listed below.

Information on previous inadequate response on MTX therapy for RA within 2 years prior to screening should be recorded with approximate dates of use (year, duration in months) and dose.

In case additional concomitant medications need to be administered or dose adjustments for pre-existing conditions (except for RA) are needed during the study, the risk/benefit to the subject should be carefully assessed by the study physician and consideration given to the timing of any necessary introduction of new medications.

If during the study, the subject's condition necessitates the use of prohibited medication, the use of IP may be interrupted, preferably after consultation with the sponsor's medical responsible. Re-introduction of IP can be considered after the treatment course with the prohibited medication has been stopped and after consultation with the sponsor's medical responsible.

During the study, subjects will be instructed to record any change in concomitant medication in a diary (see Section [8.8.1](#)).

Permitted Medications

Permitted medications at screening and during the study include:

- NSAIDs, provided that the dose is stable for at least 2 weeks prior to first IP dosing and, if possible, is kept constant during the study.
- Analgesics, other than NSAIDs, up to the maximum recommended doses may be used for pain as required.
- Oral steroids, provided that the dose is stable, at a dose of ≤ 10 mg/day prednisone or equivalent (see [Appendix 7](#) for prednisolone conversion table) for at least 4 weeks prior to first IP dosing, and is kept stable for the study duration.
- Medications prescribed for the treatment of comorbidities and which are not described as prohibited medications.

Prohibited Medications

Prohibited medications during the study include any DMARDs, other than background MTX, including:

- Oral or injectable gold, sulfasalazine, antimalarials, azathioprine, or D-penicillamine within 4 weeks prior to screening,
- cyclosporine within 8 weeks prior to screening,
- leflunomide within 3 months prior to screening or within 4 weeks prior to screening if after 11 days of standard cholestyramine therapy.

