Current or previous treatment with a bDMARD. Except for subjects who received bDMARDs in a single clinical study setting:

- For whom the last dose of bDMARD ≥ 6 months prior to screening (12 months for rituximab or other lymphocyte depleting agents), AND;
- For whom the bDMARD was effective, without being discontinued due to lack of efficacy.

Previous treatment during the year before screening as well as during the study, with a cytotoxic agent other than MTX, is prohibited. These agents include, but are not limited to chlorambucil, cyclophosphamide, nitrogen mustard, and other alkylating agents.

Receipt of an intra-articular or parenteral corticosteroid injection within 4 weeks prior to screening is prohibited.

Other prohibited medications and dietary/herbal products:

The following medications should be discontinued at least 2 weeks or 5 half-lives of the drug, whichever is longer, prior to the first dose of IP administration and throughout the study.

- [REDACTED]
- [REDACTED]
- [REDACTED]
- [REDACTED]
- [REDACTED]

Additional guidance the use of concomitant medications:

- [REDACTED]
- [REDACTED]
- [REDACTED]
- [REDACTED]

— [REDACTED]

■ [REDACTED]

The lists provided in [Appendix 1](#) through [Appendix 6](#) are non-exhaustive. In case of questions on concomitant medications, the sponsor's medical monitor (as per study contact list) and sponsor's medical responsible can be contacted.

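### Exclusion criterion 19 stops counting live vaccines at screening, so on its own wording one given between screening and first dose (up to 21 days) does not exclude a subject

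*Protocol*

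**What the plan says.** Criterion 19 of Protocol Section 6.2 is fully readable: "Subject was vaccinated with a live vaccine within 60 days prior to screening". The window is 60 days long and ends at screening.

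Section 5.1 sets the distance from there to dosing: "Screening period: up to 3 weeks with 1 study visit". The Schedule of Activities (Section 8.11) places screening on Day -21 to Day -1 and baseline, with first dose, on Day 1.

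Section 5.5 explains why a live vaccine matters here. It says of the drug's mechanism that "this may weaken the immune response and can potentially increase" the risk of infection, and that risk will be minimized "by implementing conservative eligibility criteria", among other measures.

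Section 6.3.2 governs prior and concomitant medication, and inclusion criterion 14 makes it binding: "Able and willing to comply with restrictions on prior and concomitant medication as described in Section 6.3.2". Its readable part covers DMARDs, biologic DMARDs, cytotoxic agents and corticosteroid injections. The items under its heading for other prohibited medications are redacted. Only the lead-in can be read, which says that the listed products "should be discontinued at least 2 weeks or 5 half-lives of the drug, whichever is longer", before first dose. No other readable text in the protocol or SAP mentions vaccines.

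**The concern.** An exclusion for recent live vaccination is meant to keep such an exposure away from the start of a drug that may weaken immunity. The days just before first dose are the ones that matter most, and criterion 19 leaves them out. Taken literally, a subject vaccinated two months before screening is excluded, while one vaccinated a week before first dose and after the screening visit is not.

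Counting back from screening is not the fault in itself, since criteria 1a to 1c, 2a, 3, 4 and 16 do the same. The fault is that nothing in criterion 19 looks forward from that visit. Criterion 4, on surgery, shows how the protocol can do both: "within 12 weeks prior to screening or likely requirement for surgery during the study".

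What is at stake is subject safety, in a study that plans 25 subjects with 15 on GLPG3970.

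**Working it through.** The check needs a reading of the criterion and some day counting. The plan states no figure of its own on this point to reproduce.

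**Inputs**
- Look-back: 60 days, ending at screening (Protocol 6.2, criterion 19).
- Screening visit: Day -21 to Day -1 (Protocol 5.1 and 8.11); 3 weeks × 7 = 21 days.
- First dose: Day 1. Under SAP 4.3.1 there is no Day 0, and a date before first dose is counted as that date minus the first-dose date. Day -21 is therefore 21 days before first dose.

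**Formula.** If screening is *s* days before first dose, criterion 19 excludes vaccines given *s* to *s* + 60 days before first dose. Anything given after the screening visit is not excluded.

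| Screening day | Excluded (days before first dose) | Not excluded by criterion 19 |
|---|---|---|
| Day -21 (*s* = 21) | 21 to 21 + 60 = 81 | 0 to 20 |
| Day -1 (*s* = 1) | 1 to 1 + 60 = 61 | after the screening visit, about 1 day |

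**Do other readable provisions close the interval?**
- *Recheck at Visit 1 (Section 8.11).* Inclusion and exclusion criteria are checked again, but criterion 19 still refers to screening, so a vaccine given after that visit still does not meet it.
- *New medication (Section 6.3.2).* The risk and benefit of adding a medicine "should be carefully assessed by the study physician and consideration given to the timing". This is a matter of judgement and does not bar the vaccine.
- *Subject diary (Section 8.8.1).* Changes in medication are recorded from consent onwards, but recording excludes nobody.
- *Criteria 11 and 13.* The investigator may decline a subject on judgement. Neither names vaccines.

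**Range by assumption about the redacted text of 6.3.2, with screening on Day -21**
- It bars live vaccines from consent: 0 days open.
- It lists them only under the readable 2-week lead-in: 21 − 14 = 7 days open (Day -21 to Day -15). That lead-in is about discontinuing medication and suits a single vaccination poorly, so this case is the least natural of the three.
- It is silent on them: up to 21 days open.

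**Check of the obvious alternative.** Moving the 60 days to first dose would exclude 0 to 60 days and, with screening on Day -21, newly admit 61 to 81 days. For example, a vaccine given 50 days before a Day -21 screening is 50 + 21 = 71 days before first dose: excluded now, admitted then. Keeping the look-back and extending it forward excludes 0 to 81 days.

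**The case against.** The strongest objection is that the consequence depends on text nobody outside the sponsor can read. Every item under other prohibited medications and additional guidance in 6.3.2 is redacted, the medication lists in Appendices 1 to 6 cannot be read, and some risk-mitigation bullets in Section 5.5 are blacked out. For medicines, the protocol often splits the work: Section 6.2 looks back from screening and Section 6.3.2 governs what follows, as it does for DMARDs. A live vaccine would fit naturally into the second part. Surgery, by contrast, is not a matter for a medication section, so criterion 4 needed its own forward clause and is an imperfect comparison. A disclosed vaccination would also probably reach a physician before dosing, through the diary or the medication review.

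Most of this stands as a limit on the claim. It cannot be said that the protocol as a whole permits a live vaccine in this interval. The split is not universal, however: the readable text on corticosteroid injections in 6.3.2 only looks back from screening. None of the objection changes what criterion 19 says. Even if 6.3.2 covers the interval, someone working from the exclusion list finds a vaccine rule that stops short of first dose and does not point to the rest.

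**Conclusion.** The point holds as a statement about criterion 19. Its window closes at screening, and it leaves open about 1 day (screening on Day -1) to 21 days (screening on Day -21) immediately before first dose. Whether that is a real gap in the protocol depends on the redacted parts of 6.3.2 and related text: from 0 days if they bar live vaccines from consent to 21 days if they are silent. The reading of the criterion is firm; the existence of an actual safety gap is uncertain.

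With 25 planned subjects, such a vaccination would be rare, and the documents give neither a vaccination frequency nor an infection risk from which to estimate harm. Nothing in the primary endpoint, the analysis or the sample size is touched. This is a cheap improvement to a safety criterion.

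**What to change.** Leave the existing sentence of criterion 19 as it is and append: *or at any time between screening and first IP dosing, or is planned to receive a live vaccine during the study*. Make Section 6.3.2 consistent with it. If 6.3.2 already bars live vaccines from consent onwards, a cross-reference to it in criterion 19 is enough.

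The cost is one line of protocol wording, plus an occasional screen failure or delayed vaccination.
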